4.1.2 Secondary Endpoint(s)

All Patients:

- Change in quality of life as measured with Quality of Life in Childhood Epilepsy (QOLCE) if 18 years of age or younger, or Quality of Life in Epilepsy (QOLIE) if 19 years of age or older, relative to the pre-randomization baseline of the Core Study, if assessed during the Core Study.
- Change in Subject/Caregiver Global Impression of Change (S/CGIC), relative to the pre-randomization baseline of the Core Study.
- Change in adaptive behavior as measured with the Vineland Adaptive Behavior Scales, Second Edition (Vineland-II), relative to the pre-randomization baseline of the Core Study, if assessed during the Core Study.
- Change in the number of inpatient epilepsy-related hospitalizations (number of hospitalizations due to epilepsy in each 28-day period), relative to the pre-randomization baseline of the Core Study.
- Change in the use of rescue medication (number of days used in each 28-day period), relative to the pre-randomization baseline of the Core Study.
- Maintenance of seizure frequency reduction and freedom from seizures during the OLE study.
- Percentage change in the frequency of total seizures, relative to the pre-randomization baseline of the Core Study.
- Number of patients considered treatment responders, defined as those with a $\geq 25\%$, $\geq 50\%$, $\geq 75\%$, or 100% reduction in total seizures, relative to the pre-randomization baseline of the Core Study.
- Number of patients experiencing a $> 25\%$ worsening, $- 25$ to $+ 25\%$ no change, $25-50\%$ improvement, $50-75\%$ improvement or $> 75\%$ improvement in total seizures, relative to the pre-randomization baseline of the Core Study.
- Percentage change in the frequencies of subtypes of seizures, relative to the pre-randomization baseline of the Core Study.
- Changes in duration of seizure subtypes as assessed by the Subject/Caregiver Global Impression of Change in Seizure Duration (S/CGICSD), relative to the pre-randomization baseline of the Core Study.
- Change in the number of episodes of *status epilepticus*, relative to the pre-randomization baseline of the Core Study.
- Change in cognitive function as measured with a cognitive assessment battery, relative to the pre-randomization baseline of the Core Study, if assessed during the Core Study.

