9.1.12 Patient Diary

Seizure information (number and type of seizures) will continue to be collected through an IVRS telephone diary, completed weekly until the ‘End of Treatment’/Withdrawal visit. In addition, patients/caregivers will be instructed to complete the diary using IVRS at the following times:

- Once on the day before the ‘End of Taper Period’ visit.
- Once on the day before the Follow-up visit.

The patient or their caregiver will also continue to complete a paper diary daily to record daily usage of IMP, rescue medication, concomitant AEDs and AEs. Adequate training will be provided to the patient/caregiver in order to ensure data is being accurately collated via IVRS and paper diaries.

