13.1 Sample Size, Power and Significance Levels

As this is an open label safety study, there is no formal sample size calculation. All patients who wish to continue on IMP from the populations included in the double-blind Phase 2 and Phase 3 Core Studies in DS and LGS will be eligible for inclusion. Approximately 680 patients will be enrolled.

All data collected during this study will be summarized across time, using appropriate descriptive statistical methods. There will be no formal hypothesis testing.

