2.2 Secondary

All Patients:

To evaluate the effect of GWP42003-P, as adjunctive treatment, on:

- Quality of life.

- Adaptive behavior.
- Need for hospitalizations due to epilepsy.
- Usage of rescue medication.
- Maintenance of seizure frequency reduction and freedom from seizures during the OLE study.
- Frequency of total and subtypes of seizures.
- Change in duration of subtypes of seizures.
- Number of episodes of status epilepticus.
- Cognitive function.
- Growth and development.
- Menstruation cycles (in females).
- Signals indicating drug abuse liability of GWP42003-P.

DS Patients Only:

To evaluate the effect of GWP42003-P, as adjunctive treatment, on:

- Total convulsive seizure frequency.
- Total non-convulsive seizure frequency.
- Number of patients convulsive seizure-free.
- Responder rate (defined in terms of percentage reduction in total convulsive seizure frequency).

LGS Patients Only:

To evaluate the effect of GWP42003-P, as adjunctive treatment, on:

- Drop seizure frequency.
- Non-drop seizure frequency.
- Number of patients drop seizure-free.

Responder rate (defined in terms of percentage reduction in drop seizure frequency).

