3.3.2 Secondary Endpoints

All Patients:

- Change in quality of life as measured with Quality of Life in Childhood Epilepsy (QOLCE) if 18 years of age or younger, or Quality of Life in Epilepsy (QOLIE) if 19 years of age or older, relative to the pre-randomization baseline of the Core Study, if assessed during the Core Study.
- Change in Subject/Caregiver Global Impression of Change (S/CGIC), relative to the pre-randomization baseline of the Core Study.
- Change in adaptive behavior as measured with the Vineland Adaptive Behavior Scales, Second Edition (Vineland-II), relative to the pre-randomization baseline of the Core Study, if assessed during the Core Study.
- Change in the number of inpatient epilepsy-related hospitalizations (number of hospitalizations due to epilepsy in each 28-day period), relative to the pre-randomization baseline of the Core Study.
- Change in the use of rescue medication (number of days used in each 28-day period), relative to the pre-randomization baseline of the Core Study.
- Maintenance of seizure frequency reduction and freedom from seizures during the OLE study.
- Percentage change in the frequency of total seizures, relative to the pre-randomization baseline of the Core Study.
- Number of patients considered treatment responders, defined as those with a $\geq 25\%$, $\geq 50\%$, $\geq 75\%$, or 100% reduction in total seizures, relative to the pre-randomization baseline of the Core Study.
- Number of patients experiencing a $> 25\%$ worsening, $- 25$ to $+ 25\%$ no change, 25 – 50% improvement, 50 – 75% improvement or $> 75\%$ improvement in total seizures, relative to the pre-randomization baseline of the Core Study.
- Percentage change in the frequencies of subtypes of seizures, relative to the pre-randomization baseline of the Core Study.
- Changes in duration of seizure subtypes as assessed by the Subject/Caregiver Global Impression of Change in Seizure Duration (S/CGICSD), relative to the pre-randomization baseline of the Core Study.
- Change in the number of episodes of status epilepticus, relative to the pre-randomization baseline of the Core Study.
- Change in cognitive function as measured with a cognitive assessment battery, relative to the pre-randomization baseline of the Core Study, if assessed during the Core Study.

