4.7 Changes in the Conduct of the Study or Planned Analysis

A number of additional summaries have been added, compared to the protocol, and are described in the sections above. These additions are not detailed in this section.

The following endpoints described in the protocol are not included as part of the planned analysis in this SAP due to the nature of the collection of data for the endpoint not being compatible with a continuous summary of change from baseline:

- Change in the number of inpatient epilepsy-related hospitalizations (number of hospitalizations due to epilepsy in each 28-day period), relative to the pre randomization baseline of the Core Study.
- Change in the use of rescue medication (number of days used in each 28 day period), relative to the pre-randomization baseline of the Core Study.
- Change in the number of episodes of status epilepticus, relative to the pre randomization baseline of the Core Study.

The following endpoints described in the protocol are not included as part of the planned analysis in this SAP as they were not deemed necessary for the assessment of the objectives of this trial:

- Number of patients experiencing a > 25% worsening, – 25 to + 25% no change, 25–50% improvement, 50–75% improvement or > 75% improvement in total seizures, relative to the pre-randomization baseline of the Core Study.
- Percentage change in the frequencies of subtypes of seizures, relative to the pre-randomization baseline of the Core Study.
- Percentage change in total non-convulsive seizure frequency, relative to the pre-randomization baseline of the Core Study.
- Number of patients experiencing a > 25% worsening, – 25 to + 25% no change, 25–50% improvement, 50–75% improvement or > 75% improvement in convulsive seizures, relative to the pre-randomization baseline of the Core Study.
- Percentage change in the number of non-drop seizures, relative to the pre-randomization baseline of the Core Study.
- Number of patients experiencing a > 25% worsening, – 25 to + 25% no change, 25–50% improvement, 50–75% improvement or > 75% improvement in drop seizures, relative to the pre-randomization baseline of the Core Study.

In addition, the protocol included summaries of medical history. However, this was not collected as part of the OLE and is reported as part of the core studies only.

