Appendix 5 List of Tables, Listings and Figures

Lists of the tables, listings and figures to be provided are given below in [Table 12](#), [Table 13](#) respectively

Table 12 List of Tables

Table Number	Title	Analysis Set
Table 1.1	Summary of Patient Disposition – Numbers of Patients Enrolled, Withdrawn or Completed by Site	All Enrolled Patients
Table 1.2	Summary of Patient Disposition – Primary Reason for Withdrawals	All Enrolled Patients
Table 1.3	Summary of Withdrawals by Core Study and Visit	Safety Analysis Set
Table 2.1	Summary of Important Protocol Deviations	All Enrolled Patients
Table 2.2	Summary of Analysis Sets	All Enrolled Patients
Table 3.1	Summary of Demographic Data	Safety Analysis Set
Table 3.2	Summary of Baseline Characteristics	Safety Analysis Set
Table 5.1	Summary of Previous Significant Non-Epilepsy Medical or Surgical History Now Resolved	Safety Analysis Set
Table 5.2	Summary of Significant Non-Epilepsy Medical or Surgical History – Current Conditions	Safety Analysis Set
Table 6.1	Summary of Concomitant Antiepileptic Therapies	Safety Analysis Set
Table 6.2	Summary of Concomitant Antiepileptic Medications	Safety Analysis Set
Table 6.3	Summary of Concomitant Rescue Medications	Safety Analysis Set
Table 6.4	Summary of Other Concomitant Medications	Safety Analysis Set
Table 9.1.1.1	Summary of Total Seizure Frequency	Safety Analysis Set
Table 9.1.1.2	Summary of Total Seizure Frequency (LOCF)	Safety Analysis Set
Table 9.1.2.1	Summary of Drop Seizure Frequency	Safety Analysis Set
Table 9.1.2.2	Summary of Drop Seizure Frequency (LOCF)	Safety Analysis Set
Table 9.1.3.1	Summary of Convulsive Seizure Frequency	Safety Analysis Set
Table 9.1.3.2	Summary of Convulsive Seizure Frequency (LOCF)	Safety Analysis Set
Table 9.2	Summary of Patients with Status Epilepticus	Safety Analysis Set
Table 9.3.1	Summary of the Subject/Caregiver Global Impression of Change	Safety Analysis Set
Table 9.3.2	Summary of Subject/Caregiver Global Impression of Change in Seizure Duration	Safety Analysis Set
Table 9.4.1.1	Summary of Total Seizure Frequency - Patients Taking Clobazam	Safety Analysis Set
Table 9.4.1.2	Summary of Total Seizure Frequency - Patients Not Taking Clobazam	Safety Analysis Set
Table 9.4.2.1	Summary of Drop Seizure Frequency - Patients Taking Clobazam	Safety Analysis Set
Table 9.4.2.2	Summary of Drop Seizure Frequency - Patients Not Taking Clobazam	Safety Analysis Set

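### SAP 4.7 drops the rescue-medication endpoint without saying what is incompatible, and the one summary left cannot show change

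*SAP*

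**What the plan says.** SAP 2.2 lists "Usage of rescue medication" among the secondary objectives for all patients. SAP 3.3.2 gives the matching endpoint: "Change in the use of rescue medication (number of days used in each 28-day period), relative to the pre-randomization baseline of the Core Study". Protocol 4.1.2 has the same endpoint.

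SAP 4.7 removes the analysis of this endpoint, along with those for epilepsy-related hospitalizations and status epilepticus, "due to the nature of the collection of data for the endpoint not being compatible with a continuous summary of change from baseline". It gives no further explanation.

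On collection, Protocol 9.1.12 has patients or caregivers "continue to complete a paper diary daily to record daily usage of IMP, rescue medication, concomitant AEDs and AEs". Protocol Appendix 1 schedules diary review, rescue medication included, at the clinic visits. Protocol 9.2.1 names rescue use among the Core Study diary information carried into Visit 1 for same-day enrollees. Protocol 8.2 requires every medication other than the IMP to be entered on the CRF.

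What remains is in SAP 4.5.8.10: counts and percentages by ATC term and preferred term, shown as Table 6.3, "Summary of Concomitant Rescue Medications". Listing 6.4 gives the patient-level records.

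**The concern.** The objective and the endpoint stay in the SAP, but no planned summary can answer them. Table 6.3 has no time axis, no count of days and no Core Study baseline. The reason for dropping the endpoint is not spelled out, and a daily diary set against a 28-day baseline looks like what a days-per-28-days endpoint needs.

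The seizure tables are also affected. SAP 4.5.9 reports seizure frequency by 12-week period over an extension of up to 208 weeks, during which rescue medication is allowed when necessary. Without a rescue-use summary on the same periods, a reader cannot see whether rescue use rose, fell or held steady while seizure frequency changed.

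**Working it through.** The plan gives no figure to reproduce here. Protocol 13.1 states that "there is no formal sample size calculation", and everything is descriptive. The check is a trace through the documents, followed by one illustration.

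**1. What each of the three dropped endpoints keeps**

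| Endpoint dropped in SAP 4.7 | Summary that remains | By time? | Core baseline? |
|---|---|---|---|
| Hospitalizations | Patients with any, since the previous visit (4.5.8.9) | By visit | Yes |
| Status epilepticus | Patients with seizures over 30 minutes (4.5.9.1) | By 12-week period | Not stated |
| Rescue medication | Patients by ATC and preferred term (4.5.8.10, Table 6.3) | No | No |

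The stated reason rules out a continuous summary of change. It does not rule out a count of patients by period, which the SAP itself uses for the other two.

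**2. What Table 6.3 counts.** Under 4.5.8.10 a medication is concomitant if it starts on or after the first extension dose, or started earlier and is ongoing. A standing as-needed entry carried over from the Core Study could therefore count whatever its actual use.

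**3. Illustration of why an ever-used count cannot show change.** The documents give no rates of rescue use, so those below are assumed. Let m be mean rescue days per 28 days and t the number of 28-day periods (12 weeks = 3, 104 weeks = 26, 208 weeks = 52).

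- Same rate for every patient (Poisson): share with any use = 1 − exp(−m·t).
- Rates varying between patients (gamma, shape k): share = 1 − (k / (k + m·t))^k.

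Suppose use halves, from m = 1 at baseline to m = 0.5 in the extension:

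| Model | 28-day baseline | 28-day window in extension | 12 weeks | 104 weeks | 208 weeks |
|---|---|---|---|---|---|
| Poisson | 63.2% | 39.3% | 77.7% | about 100% | about 100% |
| Gamma, k = 0.5 | 42.3% | 29.3% | 50.0% | 80.8% | 86.3% |

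Worked example, k = 0.5 at 104 weeks: m·t = 0.5 × 26 = 13, and 1 − (0.5/13.5)^0.5 = 0.808.

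The window of equal length shows the fall; the cumulative count shows a rise. The same happened for all baseline rates tried from 0.25 to 4 days per 28 days, under Poisson and under k = 0.25, 0.5 and 1: with use halved, the ever-used share at 12 weeks or later always exceeded the 28-day baseline share. Hence even a 12-week percentage should not be read directly against a 28-day baseline.

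**4. Sensitivity to the model.** At 104 weeks, compare no change at m = 0.5 with a fall to m = 0.1. Poisson gives about 100% against 1 − exp(−2.6) = 92.6%. Gamma with k = 0.5 gives 80.8% against 1 − (0.5/3.1)^0.5 = 59.8%.

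**The case against.** A reader might infer that the protocol refutes the SAP's reason. The documents do not go that far. SAP 1 says the plan was prepared from the protocol and the CRF, and the CRF is not shown. Protocol 16.2 classes diaries as source documents, so a daily diary on paper need not mean daily records in the database. SAP 4.5.8.10 handles all medications through start and stop dates, partial dates and ongoing status, which fits a medication log. If only log records are held, the stated reason may be true. Day-level rescue data in the Core baseline are likewise an inference, from the word for continuing in Protocol 9.1.12 and the list in 9.2.1; the Core protocols are not available. This objection stands: the reason is unexplained, not disproved.

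A reader might also infer that nearly every patient would be an ever-user, so that the table is saturated. That depends on giving every patient the same rate. With between-patient variation the share stays well below 100% (step 4), and Table 6.3 splits by drug term, which the illustration does not model. The point that survives needs no saturation: a count that accumulates over unequal and long follow-up, with no baseline beside it, does not measure change.

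Finally, the SAP declares the removal openly, Listing 6.4 keeps start and stop days by patient, and this is one of many descriptive secondary endpoints in a safety study. These limit the consequence. They do not supply a summary, and a listing is not one.

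**Conclusion.** The concern holds in a limited form. SAP 4.7 does not say what makes the data unsuitable. Rescue medication is the only one of the three endpoints dropped together that keeps no count by visit or period. As planned, the rescue-use objective in SAP 2.2 will not be answered.

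Confidence is high on the missing summary, which can be read directly from SAP 4.5.8.10 and the table list. It is only moderate on whether days per 28 days could be derived, because that depends on a CRF and Core Study data not in the documents. The percentages above illustrate direction only; they rest on assumed rates and an assumed degree of variation between patients. No primary safety conclusion, error rate or power is affected. The change should be made, but the study does not depend on it.

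**What to change.** - In SAP 4.5.8.10, add the number and percentage of patients with any rescue use in each 12-week period of 4.5.9, for DS and LGS, with the number of patients under observation in each period as the denominator.
- Where Core data allow, add the same percentage for a 28-day window in the extension, set against the 28-day Core baseline, so that the two windows are of equal length.
- If diary use was databased by day, take rescue medication off the list in 4.7 and reinstate days per 28 days with change from Core baseline.
- If it was not, state in 4.7 that only start and stop records are held, so that the reason can be followed.

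The cost is one derivation, one table and a few lines of SAP text. The drawback is that as-needed entries with wide or ongoing dates need a counting rule, fixed before the tables are run; without one, such entries would count as use in every period they span.

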Baseline	The 28-day period of the Core Study from screening to randomization.
Convulsive seizures	Tonic-clonic, tonic, clonic or atonic seizures.
Core Study	A double-blind, randomized, placebo-controlled, parallel group study of GWP42003-P in patients with DS or LGS.
Countable partial seizures	Partial/focal seizures with a motor or behavioral component that allow such seizures to be easily identified and hence counted.
Day 1	The day a patient first receives investigational medicinal product in this study.
Drop seizure	An attack or spell (atonic, tonic or tonic-clonic) involving the entire body, trunk or head that led or may have led to a fall, injury, slumping in a chair or hitting the patient's head on a surface.
Enrolled patient	Patient is considered enrolled in the study from the time of providing written informed consent/assent.
End of treatment	A maximum of 4 years' (208 weeks after Visit 1) treatment.
End of study	Last patient last visit or last contact, whichever occurs last.
IMP	Investigational Medicinal Product (Study Medication).
INR	International Normalized Ratio (INR) is a calculation made to standardize prothrombin time.
Investigator	Study Principal Investigator or a formally delegated study physician.
Non-convulsive seizures	Myoclonic, partial or absence seizures.
Non-drop seizures	Seizures that would not result in a fall or drop attack.
Status epilepticus	Any seizure lasting for 30 minutes or longer.
Subtypes of seizures	Protocol seizure subtypes can be atonic, tonic, clonic, tonic-clonic, myoclonic, absence, countable partial and other partial.

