12.6 Reporting Procedures for All Adverse Events

All AEs (including SAEs) occurring during the study will be reported on the running logs in the AE section of the CRF. This includes all events from the time following enrollment (Visit 1) to post study follow-up (Follow-up visit), whether or not attributed to IMP and observed by the Investigator or patient.

For the patient's expected seizure types, these do not routinely require documentation as AEs. However, any worsening, including change in the pattern or severity of seizures must be documented as an AE. Any AE which meets SAE criteria should still be reported as a SAE.

The following information will need to be provided for all AEs:

A) Adverse Event (Diagnosis or Syndrome if Known, or Signs and Symptoms)

Where the Investigator cannot determine a diagnosis, signs or symptoms should be recorded on the AE section of the CRF. Once a diagnosis has been determined the AE section of CRF must be updated to reflect the diagnosis in replacement of the original symptoms. In circumstances, where only a provisional diagnosis is possible (working diagnosis), the CRF must be updated to reflect the provisional diagnosis in replacement of the original symptoms. In some circumstances it may be relevant for the Investigator to include the symptoms alongside the diagnosis in the verbatim event description. However, the diagnosis (full or provisional) should be clearly stated e.g., fever and malaise due to a respiratory tract infection.

B) Adverse Event Start Date and Stop Date

The start and stop dates of the event must be provided. All AEs require these fields to be completed in full. Partial dates or missing dates are not normally acceptable and significant effort must be undertaken to obtain any unknown information. If a precise date is not known an estimated date should be provided instead. When a complete date cannot be given then record as much information as possible (i.e., month and year or in exceptional circumstances just year). When the actual start date becomes known the CRF must be updated to replace the previously recorded date.

C) Outcome

The outcome of the event must be recorded accurately and classified into one of the following categories:

- Recovered.
- Recovered with sequelae.
- Continuing.

- Patient died.

D) Severity

When describing the severity of an AE the terms mild, moderate, or severe should be used. Clinical judgment should be used when determining which severity applies to any AE.

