4.5 Safety and Efficacy Analysis

The safety of GWP42003-P is the primary endpoint and the aim of this study is to evaluate long term safety and tolerability and as such, there will be no formal hypothesis testing. Endpoints will be summarized as detailed in the following sections.

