4.5.9.1 Status Epilepticus

The number of convulsive seizures greater than 30 minutes in duration and the number of non-convulsive seizures greater than 30 minutes in duration will be collected weekly via IVRS.

The number of patients with convulsive and non-convulsive seizures greater than 30 minutes in duration will be presented for each of the periods mentioned in Section 4.5.9.

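### SAP 4.7 drops the only planned count of patients whose diary seizure frequency worsened by more than 25%, and the baseline comparison for status epilepticus on a reason that sits poorly with SAP 4.5.9 and 4.5.9.1

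*SAP*

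**What the plan says.** **Endpoints and objectives.** Protocol 4.1.2 and SAP 3.3.2 list a five-level classification of change from the core-study baseline, from more than 25% worsening through no change to more than 75% improvement, separately for total, convulsive and drop seizures. Both also list the change in the number of status epilepticus episodes. SAP 2.1 makes long-term safety and tolerability the primary objective; SAP 2.2 keeps the number of status epilepticus episodes as a secondary objective.

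**What is dropped.** SAP 4.7 removes the three classifications "as they were not deemed necessary for the assessment of the objectives of this trial". It removes the change in status epilepticus episodes for a different reason: "due to the nature of the collection of data for the endpoint not being compatible with a continuous summary of change from baseline".

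**What is kept.** SAP 4.5.9 keeps raw seizure frequency and percentage change, plus the number of patients with reductions of at least 25%, 50%, 75% and of 100% (Tables 9.7.1 to 9.7.6). SAP 4.1 adds quartiles to the mean, SD, median, minimum and maximum. For prolonged seizures, SAP 4.5.9.1 says that the numbers of convulsive and "non-convulsive seizures greater than 30 minutes in duration will be collected weekly via IVRS"; Table 9.2 then reports the number of patients with such seizures in each 12-week period.

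**Adverse events and definition.** Protocol 12.6 does not routinely require expected seizure types to be recorded as adverse events, but "any worsening, including change in the pattern or severity of seizures must be documented as an AE". The protocol's Definition of Terms defines status epilepticus as "Any seizure lasting for 30 minutes or longer"; SAP 4.5.9.1 counts only seizures of more than 30 minutes.

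**The concern.** In a single-arm, open-label safety study, the categorical display of seizure frequency should run in both directions. As planned, anyone with less than a 25% reduction, whether unchanged or much worse, falls into one undivided remainder. Aggravation by an antiepileptic drug is not far-fetched here: Protocol 3.1 itself notes that lamotrigine can worsen seizures in Dravet patients. Adverse-event reporting of worsening is mandatory but carries no numerical threshold, so it depends on site judgement and does not replace a count from the diary.

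For status epilepticus, the stated objective is the number of episodes, yet the planned table counts patients. A patient with six episodes in a period counts the same as a patient with one, and no column shows whether the frequency rose or fell from baseline.

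**Working it through.** The plan has no figure to reproduce: "As this is an open label safety study, there is no formal sample size calculation", and "there will be no formal hypothesis testing". The check is whether the retained output can give the dropped numbers.

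**1. How many could worsen without moving the upper quartile.** While fewer than about a quarter of patients worsen by more than 25%, the upper quartile of percentage change need not exceed +25%.

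- Protocol 13.1: "Approximately 680 patients will be enrolled". SAP Table 1 gives 34 randomized in GWEP1332 Part A, which SAP 4.5.9 excludes from seizure summaries. 680 − 34 = 646, taken as about 640 (assumption). 640 × 0.25 = 160.
- By indication, randomized outside Part A: Dravet 120 + 199 = 319; LGS 171 + 225 = 396. If all enter, the limits are about 79 and 98, together 177.
- If 680 of the 749 randomized enter, at the same rate in each study (assumption), there are about 290 Dravet and 360 LGS patients, with limits of about 72 and 89, together 161.

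**2. Two hypothetical groups of 360.** Both have 18 patients at −100%, 72 at −80%, 90 at −60% and 54 at −30%. The other 126 differ:

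- Group A: 125 at 0%, one at +200%.
- Group B: 38 at 0%, 87 at +60%, one at +200%.

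| Statistic | A | B |
|---|---|---|
| Reduction of at least 25 / 50 / 75 / 100% | 65 / 50 / 25 / 5% | 65 / 50 / 25 / 5% |
| Minimum, Q1, median, Q3, maximum | −100, −65, −45, 0, +200 | −100, −65, −45, 0, +200 |
| Mean (SD) | −39.9 (36.5) | −25.4 (56.2) |
| Worsened by more than 25% | 1 (0.3%) | 88 (24.4%) |

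Only the mean and SD differ.

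**3. Mean and SD do not settle the count either.** In group B, replace the 87 values of +60% by 29 sets of three. The set (+20, +20, +50) has sum 90 and sum of squares 400 + 400 + 2,500 = 3,300. The set (+10, +40, +40) has sum 90 and sum of squares 100 + 1,600 + 1,600 = 3,300. All values lie above Q3 and below the maximum, so every retained statistic, including mean and SD, is the same under either choice. The number worsened by more than 25% is 29 + 1 = 30 (8.3%) in one case and 29 × 2 + 1 = 59 (16.4%) in the other.

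**4. The reason given for status epilepticus, set against the rest of the SAP.** SAP 4.5.9.1 collects a weekly count by IVRS. SAP 4.5.9 turns weekly IVRS seizure counts into 28-day rates and compares them with core-study counts recorded daily. SAP 4.1.4.1 defines a core baseline for IVRS endpoints. Epilepsy hospitalizations were dropped as a change endpoint for the same stated reason, yet SAP 4.5.8.9 still gives them a baseline column; SAP 4.5.9.1 plans none.

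**5. Why a baseline percentage alone would mislead in Table 9.2.** The protocol's baseline is 28 days and the reporting periods are 84 days. At a constant rate of 0.1 episodes per 28 days (illustrative; the documents give no rate) and a Poisson count, the chance of at least one episode is 1 − exp(−0.1) = 9.5% in 28 days and 1 − exp(−0.3) = 25.9% in 84 days. With nothing changed, the percentage would appear to rise almost threefold. A rate per 28 days avoids this.

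**The case against.** A reader might infer that the tables hide seizure-related harm. The documents do not support that. Percentage change is reported in both directions, by 12-week period, for the last 12 weeks and in subgroups. Table 9.2 shows patients with prolonged seizures. S/CGIC has three worse categories, and S/CGICSD has one for increased duration, judged against core baseline under Protocol 9.1.11.4. Table 14.3 gives epilepsy hospitalizations with a baseline. Recorded worsening feeds the TEAE tables and, where criteria are met, the serious and discontinuation tables. Listings 9.2 and 9.3 hold patient-level data. The number with less than a 25% reduction also follows by subtraction from the responder table; only its split is missing.

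The classifications are secondary endpoints. The primary safety endpoint (Protocol 4.1.1) is untouched, the study is descriptive, and the change is declared openly. All of this stands and limits the weight of the point.

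A reader might also infer that SAP 4.5.9.1 contradicts SAP 4.7 on status epilepticus. That is not proven: SAP 4.5.9.1 describes collection in the extension, and neither document says how prolonged seizures were recorded at core baseline. If the core studies hold no matching count, the stated reason could be sound, though unexplained.

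Finally, the 30-minute limit may be fixed by the IVRS question, in which case SAP wording cannot recover seizures of exactly 30 minutes.

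None of these outputs supplies the dropped count of patients beyond a set threshold of worsening.

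**Conclusion.** The point holds in limited form. SAP 4.7 removes the only planned count of patients whose diary seizure frequency worsened by more than 25%, while SAP 3.3.2 still lists it as an endpoint. The responder tables run one way, and the retained statistics cannot recover the number. The limit of about 160 patients (about 161 to 177 when worked by indication) rests on the assumed numbers entering; it bounds what can stay below the upper quartile and says nothing about how many will worsen.

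For status epilepticus, the stated reason sits poorly with the SAP's own weekly counts and 28-day rates, and Table 9.2 does not report the objective's number of episodes. Confidence is high on the worsening rows and lower on the baseline comparison, which depends on what the core studies recorded. The change should be made, but it does not undermine the study's primary safety analysis.

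**What to change.** - **Tables 9.7.1, 9.7.3 and 9.7.5, and LOCF versions 9.7.2, 9.7.4 and 9.7.6:** add one row for an increase of more than 25% and one for no change, running from less than a 25% reduction up to and including a 25% increase. A reduction of exactly 25% counts as a responder, so the rows do not overlap.
- **Table 9.2:** add status epilepticus episodes per 28 days for each 12-week period and the last 12 weeks. Add core baseline and change where the core studies hold the same count; otherwise state in SAP 4.7 which baseline data are lacking.
- **SAP 4.7:** amend to match.
- **Duration limit:** reconcile the protocol definition with SAP 4.5.9.1, or state that the IVRS item fixes the limit.

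The cost is a few extra rows from seizure data already collected, plus SAP wording. The reported profile may look slightly less favourable.
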